10.1.4 Measurement Time Points

ECG will be assessed on a twice weekly basis during treatment, a baseline troponin at the initiation of the study, and physical examination weekly during treatment. Follow up will take place with

physical examination and a clinic visit monthly after treatment.

10.1.5 Response Review

Not applicable.

10.2 Secondary Outcome: Efficacy

10.2.1 Relevant Subset

Patients in the Phase II study will be evaluated for PFS 6 months after completion of chemoradiation

10.2.2 Measurement Definition

This endpoint of PFS6 months post start of chemoradiation will be assessed using RANO criteria.

10.2.3 Measurement Methods

Endpoint will be measured based on the RANO criteria, using both clinical examinations and MRIs with and without contrast.

Complete Response (CR): Requires all of the following:

- Complete disappearance of all enhancing measurable and non-measurable disease
- Stable or improved non-enhancing (T2/FLAIR) lesions
- No new lesions
- Off corticosteroids (or on physiologic replacement dose)
- Stable or improved clinical status

Partial Response (PR): Requires all of the following:

- ≥ 50% decrease compared with baseline in the sum of the products of the diameter (SPD) of measurable enhancing target lesions
- No progression of non-target disease (enhancing and non-enhancing (T2/FLAIR) lesions)
- No new lesions
- Corticosteroid dose stable or decreased
- Stable or improved clinical status

Stable Disease (SD): Requires all of the following:

- Does not qualify for CR, PR or PD
- Stable non-enhancing (T2/FLAIR) lesions
- Corticosteroid dose not increased > 50%
- Stable or improved clinical status

Progressive Disease (PD): Requires any of the following

- \geq 25% increase in the SPD of measurable enhancing target lesions plus >5 mm absolute increase in the sum of the longest diameters (SLD) of target lesions compared to the best response after initiation of therapy
- Clear progression of enhancing non-target disease
- Significant increase in T2/FLAIR non-enhancing disease not caused by co-morbid events (eg radiation therapy, demyelination, ischemic injury, infection, seizures, post-operative changes or other treatment effects)

- Any new lesions
- Clear clinical deterioration not attributable to other causes apart from the tumor (eg, seizures, medication adverse effects, complications of therapy, cerebrovascular events, infections etc)
- Increasing steroid doses alone do not constitute PD.

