10.2.4 Measurement Time Points

An MRI will be done 35+/-3 days after the completion of XRT. Follow up MRIs will be done per standard of care (approximately every 8-12 weeks), with one occurring 6 months post the start of radiation, until progression or withdrawal of consent.

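### The progression list in section 10.2.3 excludes treatment effects for T2/FLAIR and clinical change but not for enhancing or new lesions, so treatment-related change on the first post-radiation MRI can count as a PFS6 failure

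*Combined protocol and SAP*

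**What the plan says.** The combined protocol and SAP sets the Phase II endpoint in section 10.2.3: "Endpoint will be measured based on the RANO criteria, using both clinical examinations and MRIs with and without contrast". It then writes out its own response categories. The progression entry opens "Progressive Disease (PD): Requires any of the following", so one item is enough. The items treat non-tumour causes differently:

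- **Enhancing target lesions:** "25% increase in the SPD of measurable enhancing target lesions", together with an absolute increase of more than 5 mm in summed diameters, "compared to the best response after initiation of therapy". No exclusion.
- **Enhancing non-target lesions:** "Clear progression of enhancing non-target disease". No exclusion.
- **New lesions:** any new lesion counts. No size threshold, no exclusion.
- **T2/FLAIR:** "Significant increase in T2/FLAIR non-enhancing disease not caused by co-morbid events (eg radiation therapy, demyelination, ischemic injury", and the list goes on to other treatment effects. Excluded.
- **Clinical decline:** causes other than the tumour are excluded, including complications of therapy.

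On timing, section 10.2.4 states "An MRI will be done 35+/-3 days after the completion of XRT", whereas section 4 puts that scan 4 weeks after radiation, plus or minus 7 days. Later MRIs follow routine practice, about every 8 to 12 weeks, with one at 6 months from the start of radiation. Section 10.2.4 ends them at progression. Under section 10.2.5, delegated investigators read the scans.

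**The concern.** The plan recognises that radiation and other therapy can imitate progression, but it acts on this for only two kinds of change. Enhancing and new lesions are left out, although section 2.4 directs a boost to 60 Gy at the enhancing area. The first scan follows a few weeks later and one reading settles the matter.

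At stake is the Phase II primary endpoint in 20 patients. Wrongly recorded failures pull the observed PFS6 down towards the 50% benchmark and could hide a real effect. The plan does not ensure that later images correct the record. Section 10.2.4 stops MRIs at progression, section 4.2 lists progression as a reason for discontinuation or withdrawal, and post-progression follow-up in section 4 collects survival and subsequent therapy only.

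**Working it through.** **1. Is the early scan inside the PFS6 window?** Radiation lasts 6 weeks (section 2.4).

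- Section 4: 6 + (4 ± 1) = week 9 to 11 from the start of radiation.
- Section 10.2.4: (42 + 32)/7 = 10.6 to (42 + 38)/7 = 11.4 weeks.
- Six months is about week 26, and the 6-month MRI with its ± 2 weeks is at week 24 to 28.

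The scan is well inside the window. This holds whether the clock starts with radiation (sections 1.1 and 10.2.2) or at its completion (section 10.2.1).

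**2. Is there a routine scan that could confirm?** Adding 8 to 12 weeks to week 9 to 11 gives week 17 to 23, before the 6-month MRI. It exists on the schedule, but it is not assured once progression has been called.

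**3. Which items can act on the first scan?** The non-target and new-lesion items can. For the 25% rule the answer is unclear. Its comparator is the best response since therapy began, and no earlier on-therapy MRI is scheduled. Either the rule cannot act at that scan, or it falls back on pre-radiation imaging without saying so.

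**4. How large could the effect be?** There is no figure in the plan to reproduce: section 12.6.2 asserts power without a number, and no alpha, sidedness, test or alternative rate is given. From the plan: n = 20 (section 12.5.1) and a 50% benchmark (section 12.5.2). Assumed: true PFS6 p = 75%, and a share q of true successes wrongly called progression.

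Observed rate = p(1 − q). Chance of a positive result = P(X ≥ k), with X binomial (20, p(1 − q)).

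Two cut-offs are shown. For a one-sided exact 5% test, P(X ≥ 14 | 0.5) = 0.0577 and P(X ≥ 15 | 0.5) = 0.0207, so k = 15. For the synopsis rule of more than 50%, k = 11.

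| q | Successes lost (of 15 expected) | Observed PFS6 | 15 or more of 20 | 11 or more of 20 |
|---|---|---|---|---|
| 0 | 0 | 75% | 61.7% | 98.6% |
| 5% | 0.75 | 71.25% | 46.5% | 96.4% |
| 10% | 1.5 | 67.5% | 32.5% | 92.1% |
| 20% | 3 | 60% | 12.6% | 75.5% |

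**5. Could a confirmed-only rule err the other way?** Suppose the historical 50% was itself measured with unconfirmed progression and the same q. A regimen with no effect would then read 0.5/(1 − q) once confirmation is required: 52.6%, 55.6% or 62.5%. The chance of 15 or more of 20 would rise from 2.1% to 3.5%, 6.1% or 17.9%.

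**The case against.** The strongest reply is that the endpoint rests on RANO by name and that investigators judge progression (sections 4.2 and 10.2.5), so an experienced reader could discount treatment effects anyway. That is possible. But section 10.2.3 writes its own list, with exclusions on two items only, and no section supplies one for the rest. Relying on an unwritten provision leaves the handling to each reader.

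The thresholds also give some protection: 25% plus 5 mm for target lesions, and a requirement that non-target progression be clear. They filter small changes, not changes from a non-tumour cause, and new lesions have no threshold.

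Several stronger readings are tempting and are not supported:

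- *Every such patient is a certain PFS6 failure.* Sections 12.4, 12.5.2 and 12.7 describe a status at 6 months: stable scan and clinical condition, steady steroid dose, no bevacizumab. Early enhancement that settles might pass that test.
- *The 25% rule compares the first MRI with a pre-radiation scan.* The text names best response after therapy began, and only partial response is measured from baseline.
- *The trial loses most of its power.* That depends on an assumed test and assumed misclassification rates. Under the synopsis rule the loss is much smaller.
- *The bias must run against the regimen.* Section 12.6.3 says a historical control rate was used, but not how progression was scored in it. If it counted unconfirmed progression, the present rule is the matched one.
- *Treatment effects are most likely at this scan.* The documents do not say so, and the point does not need it.

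**Conclusion.** The point stands as a gap in the endpoint definition. Followed as written, treatment-related non-target enhancement or a new lesion on the first post-radiation MRI is unconfirmed progression and can be a PFS6 failure. For target lesions the reference scan at that visit is unclear. The same patient might still meet the 6-month status benchmark in section 12, so the plan holds two incompatible ways to score the case.

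The size is illustrative only. The misclassification shares of 5% to 20%, the true rate of 75% and the one-sided 5% test are assumptions. The effect ranges from small (98.6% to 96.4% under the more-than-50% rule at 5% misclassification) to decisive (61.7% to 12.6% under the exact test at 20%). The net direction relative to the 50% benchmark cannot be settled until the derivation of that benchmark is stated.

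**What to change.** For endpoint classification only:

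1. In section 10.2.3, extend the existing treatment-effect exclusion to enhancing and new lesions on the first post-radiation MRI. Count progression on that scan towards PFS6 only if a later routine MRI (about week 17 to 23, or the 6-month scan) supports it, and then date it back to the first scan.
2. Name the reference scan for the 25% rule at that first MRI.
3. In section 10.2.4, state that routine MRIs are still collected after an unconfirmed early progression call. Say in advance how a patient is classified when no later scan exists.
4. Report PFS6 under both the unconfirmed and the confirmed rule. State which one matches how the 50% historical rate was derived, and use that one for the decision.
5. Reconcile the wording with sections 4.2, 10.2.4, 12.4, 12.5.2 and 12.7, and align the first-MRI date between sections 4 and 10.2.4. Treatment and withdrawal decisions stay with the investigator.

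The cost is endpoint wording, one additional analysis, and continued collection of routine images in a few patients. A few early classifications wait for the next routine MRI. The main risk is that a confirmed-only rule would favour the regimen if the benchmark counted unconfirmed progression, which is why step 4 ties the decision to the matching rule.

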10.2.4 Measurement Time Points

An MRI will be done 35+/-3 days after the completion of XRT. Follow up MRIs will be done per standard of care (approximately every 8-12 weeks), with one occurring 6 months post the start of radiation, until progression or withdrawal of consent.

10.2.5 Response Review

The Investigators delegated to do so, will evaluate the MRIs for response

11. REGULATORY CONSIDERATIONS

11.1 Institutional Review of Protocol

The protocol, the proposed informed consent and all forms of participant information related to the study (e.g. advertisements used to recruit participants) will be reviewed and approved by the Stanford IRB and Stanford Cancer Institute Scientific Review Committee (SRC). Any changes made to the protocol will be submitted as a modification and will be approved by the IRB prior to implementation. The Protocol Director will disseminate the protocol amendment information to all participating investigators.

11.2 Data and Safety Monitoring Plan

The Stanford Cancer Institute Data and Safety Monitoring Committee (DSMC) will be the monitoring entity for this study. The DSMC will audit study-related activities to determine whether the study has been conducted in accordance with the protocol, local standard operating procedures, FDA regulations, and Good Clinical Practice (GCP). This may include review of the following types of documents participating in the study: regulatory binders, case report forms, eligibility checklists, and source documents. In addition, the DSMC will regularly review serious adverse events and protocol deviations associated with the research to ensure the protection of human subjects. Results of the DSMC audit will be communicated to the IRB and the appropriate regulatory authorities at the time of continuing review, or in an expedited fashion, as needed.

11.3 Data Management Plan

The Protocol Director, or his designee, will prepare and maintain adequate and accurate participant case histories with observations and data pertinent to the study. Study specific Case Report Forms (CRFs) will document treatment outcomes for data analysis. Case report forms will be developed using the OnCore database system and will be maintained by CRFs will be kept in a locked office, only accessible to the research team.

12. STATISTICAL CONSIDERATIONS

in the department of Biostatistics, Health Research and Policy will serve as the primary statistician.

12.1 Statistical Design

This is a dose-escalation study with three planned dose levels using the modified toxicity probability interval (mTPI). The mTPI method is a competitor to the usual 3+3 dose escalation scheme and to the Continuous Reevaluation Method (CRM), mTPI has the advantage of having been peer-reviewed in both the statistical literature and in the oncology literature [74]. The design has the further advantage of allowing the investigators to conduct the study without constant reference to a biostatistician (as required by the CRM approach). It also allows for planned de-escalation as in this protocol

Planned dose levels are 200 μ g/kg/d x 2 wks (continuous infusion), 100 μ g/kg/d x 4 wks, 200 μ g/kg/d x 4 wks, and 400 μ g/kg/d x 4 wks. The starting total dose will be the middle dose 200 μ g/kg/d x 4 wks.

If a DLT occurs from Day 15-28, we will treat next patient with a dose of 200 μ g/kg/d x 14 days. If a DLT occurs from day 0-14, we will treat next patients at a dose of 100 μ g/kg/d x 28 days. If a patient experiences a DLT, the infusion will be discontinued. The next patient treated at the lower dose level as dictated by the mTPI table. If an early dose limiting toxicity occurs at lowest dose level,200 μ g/kg/d x 2 wk or 100 μ g/kg x 4wks, then the protocol will be stopped at that point.

The design is based on a Bayesian calculation of the posterior probability of toxicity at each dose. The following settings have been used:

- * The target toxicity level. In this study we use the same level of 30% as in [74], which also corresponds informally to the target toxicity of the 3+3 design.
- * The precision for that target toxicity (here plus or minus 5 percentage points).
- * The maximum sample size across all dose (here 9).
- * Planned dose levels 200 μ g/kg/d x 2 wks (continuous infusion), 100 μ g/kg/d x 4 wks, 200 μ g/kg/d x 4 wks and 400 μ g/kg/d x 4 wks. The starting total dose will be the middle dose 200 μ g/kg/d x 4 wks.

The prior is a beta with parameters 1 and 1 (roughly equivalent to two observations, one of these a DLT). Briefly, with the above settings, when the posterior probability falls below 0.25 (0.30-0.05), escalation to the next higher dose level is indicated; when the posterior probability falls above 0.35 (0.30+0.05), de-escalation is recommended; otherwise the next patient is to be treated at the same dose level. The rules for escalation and de-escalation for this design are contained in Table 12.1; they do not need to be modified during the course of the study. At the end of the study the toxicity data at all doses is combined using the "pool adjacent violators" algorithm to make toxicity probabilities non-decreasing; the maximum tolerated dose is calculated as the dose level that comes closest to the target toxicity level.

Table 12.1 show the action to be taken as each patient becomes evaluable for toxicity. It is used for all dose levels as follows:

- E means that the next patient is to be treated at the next higher dose. If the current dose is the highest planned $400 \mu g/kg/d \times 28 d$, the next patient is to be treated at the **same** dose level.
- S means that the next patient is to be treated at the same dose level. Note that a minimum of 3 subjects must be studied at a dose before escalation is indicated.
- D means that the next patient is to be treated at the next lower dose. If the current dose is the

- lowest planned 200 µg/kg/d x 14 d, the next patient is to be treated at the same dose level.
- U means that the current dose level is too toxic. No further patients are to be treated at this or at any higher dose level. If the current dose level is the lowest planned (200 μ g/kg/d x 2 wks total dose) no further patients will be treated. If the current dose level is not the lowest planned, the next patient should be studied at the next lowest dose (100 μ g/kg/d x 4 wks).

These definitions are in accord with our reading of the code used to produce the simulations which validated the mTPI design.

Toxicity will be monitored in the expansion phase at each increment of 5 patients. If DLT is observed in one out of the first 5 patients, or 2 of the first 10, or 2 of the first 15, toxicity will be reviewed to assess whether the trial should continue. This stopping rule has a 5% chance of being triggered if the true DLT toxicity rate is 5%, it has a 62% chance of being triggered if the true DLT rate is 30%.

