Finally, chronic administration of Plerixafor has also been evaluated by continuous infusion for 10 days in HIV patients in an open-label dose escalation study with doses ranging from 2.5 to 160 μ g/kg/h [30]. In this study, a 10 day infusion was administered via infusion pump at 40mL/hour (daily solutions prepared by dilution of a 10 mg/mL solution of Plerixafor in 0.9% saline). Note that the total dose infused in this study was much higher than those doses proposed here (i.e., the highest dose over 4 weeks for our protocol will be 11,200 mcg/kg compared to 38,400 mcg/kg total for the highest cohort in the cited study). The median terminal elimination half-life was 8.6 hours (range: 8.1-11.1 hours). Cardiac toxicities were observed in the HIV+ patients dosed to achieve C_{max} levels above 2 μ g/mL.

Plerixafor for Stem Cell Mobilization

Plerixafor is a bicyclam small molecule that selectively and reversibly inhibits CXCR4. In preclinical and clinical studies it was found to lead to a rapid increase in circulating hematopoietic progenitor cells and mature lymphocytes.

In a phase I clinical trial conducted in healthy volunteers, a single dose of Plerixafor by SC injection (160 or 240 $\mu g/kg$) given alone or added to a mobilization regimen of daily G-CSF (10 $\mu g/kg$) for four days was shown to be generally safe and well-tolerated, as compared to a mobilization regimen consisting of G-CSF alone [31]. The most frequently reported AEs were injection site reactions, GI effects, paresthesias, and headaches. Plerixafor augmented CD34+cell mobilization by G-CSF on average 3.8 fold. More recently, the safety of Plerixafor administered as a single agent by injection was further explored in healthy volunteers at doses up to 480 $\mu g/kg$ [32]. No dose limiting toxicity was observed, and common adverse events were diarrhea, injection site erythema, perioral numbness, sinus tachycardia, headache, nausea, abdominal distention and injection site pain.

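### After a DLT the Phase I rules give conflicting instructions for the next patient, because the two lowest regimens are ranked in one place and treated as jointly lowest in another

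*Combined protocol and SAP*

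**What the plan says.** Section 12.1 opens with "This is a dose-escalation study with three planned dose levels" and then lists four: "Planned dose levels are 200 μ g/kg/d x 2 wks (continuous infusion), 100 μ g/kg/d x 4 wks", followed by 200 and 400 µg/kg/d, each for 4 weeks. The start is 200 µg/kg/d x 4 weeks, called the middle dose.

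Two sets of rules then decide where the next patient goes.

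- **Table 12.1 and its action definitions (Section 12.1).** "D means that the next patient is to be treated at the next lower dose". The lowest planned level is named as 200 µg/kg/d x 14 d. D at that level means "x 14 d, the next patient is to be treated at the same dose level". For U the text reads "If the current dose level is not the lowest planned, the next patient should be studied at the next lowest dose", and the bracket after it names 100 µg/kg/d x 4 weeks.
- **Timing rule and stop (Section 6.1, repeated in Section 12.1).** A DLT in the first two weeks sends the next patients to 100 µg/kg/d x 28 d. A DLT in weeks 3 or 4 sends the next patient to 200 µg/kg/d x 14 d. The stop begins "If an early dose limiting toxicity occurs at lowest dose level", names both of these regimens, and ends the protocol. The same paragraph also sends the reader back to the mTPI table for the lower level.

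At the end of Phase I, Section 12.1 applies the pool-adjacent-violators "algorithm to make toxicity probabilities non-decreasing" and takes the level closest to 30% as the MTD.

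**The concern.** Moving one step down a list needs a list with a defensible order. For the two lowest regimens the plan gives no reason for its order, and elsewhere it treats them as alternatives at the same rung. Daily rate and duration rank them in opposite directions, and total dose does not separate them.

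The stake is the next patient's assignment just after toxicity has been seen. Depending on the sentence followed, that patient goes to another regimen, stays at the same one, or is not treated because the protocol has stopped. Section 12.1 presents the design as one that investigators can run without constant recourse to a biostatistician, so the written rules have to be enough by themselves.

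**Working it through.** **Dose arithmetic.** Total dose = daily rate x days.

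| Regimen | Daily rate (µg/kg) | Days | Total (µg/kg) |
|---|---|---|---|
| 200 x 14 d | 200 | 14 | 2,800 |
| 100 x 28 d | 100 | 28 | 2,800 |
| 200 x 28 d | 200 | 28 | 5,600 |
| 400 x 28 d | 400 | 28 | 11,200 |

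The last row reproduces the plan's own figure in Section 2.5: "the highest dose over 4 weeks for our protocol will be 11,200 mcg/kg". Along the ranking in the action definitions, D from 100 x 28 d doubles the daily rate and halves the duration, and E from 200 x 14 d does the reverse. Total dose is unchanged either way.

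**The table itself.** With a Beta(1,1) prior, target 0.30, margin 0.05, and U when the posterior probability that the DLT rate exceeds 0.30 is above 0.95 (the 0.95 is an assumption; the plan does not state it), all 54 cells of Table 12.1 are reproduced. The cells are right; the problem is the order of levels on which they act. The one-DLT row is D S S S S E E E E, so none of its 9 cells stops the trial.

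**Rules side by side.**

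| Situation | Table 12.1 and definitions | Section 6.1 and timing text of 12.1 |
|---|---|---|
| First patient at 100 x 28 d has an early DLT | D: move to 200 x 14 d | Stop |
| First patient at 200 x 14 d has an early DLT | D at lowest: same level | Stop |
| 200 x 28 d, 1 DLT in 1 patient, weeks 3 or 4 | D: move to 100 x 28 d | Move to 200 x 14 d |
| 200 x 28 d, 1 DLT in 2 to 5 patients | S: same level | Move to 100 x 28 d or 200 x 14 d by timing |
| U at 100 x 28 d, read literally | Next dose named is 100 x 28 d, the level just declared too toxic | Stop if the DLT was early |

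**Effect on the MTD.** One path through Table 12.1 uses exactly 9 patients: 2/3 DLTs at 200 x 28 d, then 1/1 at 100 x 28 d, then 0/3 at 200 x 14 d, then two more without DLT at 100 x 28 d (1/3 in all).

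- Plan's order: 0, 0.33, 0.67. The closest to 0.30 is 100 x 28 d.
- Low pair reversed: (0+1)/(3+3) = 0.17 for both, a tie. The plan has no tie-break.
- Low pair unordered, both below 200 x 28 d: 0, 0.33, 0.67. Same choice as the plan.

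All Table 12.1 paths with N = 9 were enumerated exactly, starting at 200 x 28 d, with at least 3 patients before escalation, U taken as one step down with that level and higher ones closed, and no timing rule or early stop. The DLT rates are assumptions, listed in the plan's order of levels.

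| Assumed DLT rates | Both low levels hold data | MTD set changes, low pair unordered | MTD set changes, low pair reversed |
|---|---|---|---|
| 5, 5, 10, 20% | 0.6% | 0.0% | 0.6% |
| 10, 15, 30, 50% | 7.0% | 0.02% | 6.6% |
| 20, 25, 40, 60% | 17.8% | 0.3% | 16.1% |

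No path gave MTD sets with no level in common.

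**The case against.** The best defence is that the stop applies only to an early DLT, so the texts can be read together: an early DLT at a low level stops the protocol, and a late one follows the table. On that reading a move from 100 x 28 d to 200 x 14 d follows only a late DLT and shortens exposure, which is the logic of the weeks 3–4 rule. This is coherent, but the plan does not say it. The word early is not defined at the low levels; if it means the first 14 days, every DLT during a 14-day infusion is early. Nor does this reading mend the U sentence or the conflict at 200 x 28 d.

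A second defence is that there really are three levels if levels are tiers of total dose (2,800; 5,600; 11,200), which also fits calling the start the middle dose. That stands. The count of three may be the intended one, and it is then the strict ranking in the action definitions that does not fit.

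A reader might infer that the ranking often drives the MTD. The documents do not support that. The large changes come only from fully reversing the pair, which the plan does not do, and even then the result shares a level with the plan's choice. Some striking examples cannot occur under Table 12.1 alone. With 1/2 DLTs at 200 x 14 d and 0/3 at 100 x 28 d, for instance, the 14-day level could not have been reached, because entering it takes a D or U at 100 x 28 d and hence at least one DLT there. The frequencies also ignore the early stop. If half of low-level DLTs are early (an assumption), both low levels hold data in 0.3% to 8% of trials; if all are, in none.

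**Conclusion.** The conflict is real and should be resolved. After a DLT at either low level, or at the starting level, the plan gives more than one instruction for the next patient, and one sentence taken literally returns patients to a level just declared too toxic. This rests on the text and on simple dose arithmetic, with no modelling assumption. It matters only once toxicity has occurred, since a trial that escalates cleanly never meets it.

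The pool-adjacent-violators issue is minor. The regimens themselves support only a partial order: each low level below 200 x 28 d, and that below 400 x 28 d. Ranking the low pair is unexplained rather than shown to be wrong. Remarks in Section 2.5 that link some toxicity to peak concentration do not settle the order of these two infusions. On the assumed DLT rates, dropping the ranking changes the nominated MTD set in at most about 0.3% of trials.

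**What to change.** The sponsor should reconcile three things: the E, D and U definitions in Section 12.1; the timing rule and early-DLT stop in Sections 6.1 and 12.1; and the stated number of levels. The result should be one unambiguous action for each outcome at each level. If DLT timing is to decide the destination, the text should say so, define early at the low levels, and state whether the table or the timing rule prevails. Which regimen follows, when the protocol stops, and whether there are three levels or four are for the sponsor to decide; no dose or stopping rule is proposed here.

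For the MTD, either give the reason for ranking the low pair, or run the isotonic step only along the order that the regimens support, leaving the two low levels unordered relative to each other.

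The cost is wording and a few lines of analysis code. The partial order borrows slightly less information between the two low levels.

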Once the infusion phase is completed, patients will then receive adjuvant temozolomide in standard monthly dosages (i.e., 150 mg/m² x 5 days), beginning at day 35 after finishing XRT (to ensure no overlap with Plerixafor).

Version #11, Date: 04-29-2015 CONFIDENTIAL

Phase II

If in the Phase I, patients achieve the highest AUC level (i.e., $400 \mu g/kg$ per day for 4 weeks) without significant toxicity, we will then conduct a lead-in Phase II study wherein an additional 20 patients will be enrolled so that efficacy (i.e., PFS 6) can be measured. There will be no delay between enrolling patients in this group and multiple patients can be enrolled and treated at the same time.

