6.1 Dose Limiting Toxicities

DLT is defined as any hematologic or non-hematologic AE grade ≥3 with a suspected causal relationship to Plerixafor (including including ECG changes indicative of ischemia, ventricular tachycardia).

- Patients will be monitored for DLTs for 5 weeks from the start of the Plerixafor infusion.
- DLT's in the first cohort may occur before or after 14 days. If a DLT occurs in weeks 3 or 4 of treatment, we will treat next patient with a dose of 200 μg/kg/d x2 weeks. If a DLT occurs from the start of treatment through the second week of treatment, we will

Version #11, Date: 04-29-2015 Page 27 of 52

treat next patients at a dose of 100 μ g/kg/d x 4 weeks. If a patient experiences a DLT, the infusion will be discontinued. The next patient treated at the lower dose level as dictated by the mTPI table. If an early dose limiting toxicity occurs at lowest dose level (200 μ g/kg/d x 2 wk or 100 μ g/kg x 4wks) then the protocol will be stopped at that point.

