12.5.1 Analysis Population

20 additional patients will be enrolled in the Phase II component of this study for determination of efficacy.

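### Phase II DLT limits are checked only at each block of 5 patients, so further patients can be treated after a toxicity review has already become certain

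*Combined protocol and SAP*

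**What the plan says.** Section 12.1 sets the Phase II (expansion) toxicity rule. On timing: "Toxicity will be monitored in the expansion phase at each increment of 5 patients". On the limits: "If DLT is observed in one out of the first 5 patients, or 2 of the first 10, or 2 of the first 15". On the action: "toxicity will be reviewed to assess whether the trial should continue". The same paragraph gives the rule a 5% chance of being triggered at a true DLT rate of 5%, and 62% at 30%. It states no limit for patients 16 to 20.

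Section 2.4 describes Phase II enrolment: "There will be no delay between enrolling patients in this group and multiple patients can be enrolled and treated at the same time". The gap of at least 1 week between patients, also in Section 2.4, belongs to the Phase I dose levels.

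Section 6.1 fixes the observation period: "Patients will be monitored for DLTs for 5 weeks from the start of the Plerixafor infusion". Section 12.5.1 gives the size of the phase: "20 additional patients will be enrolled in the Phase II component of this study".

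No section says whether enrolment continues once a limit has been reached, while a block completes its 5 weeks of observation, or while a review is under way. Nor does the plan say whether a block is checked when its fifth patient starts or when that patient completes observation.

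**The concern.** The limits are cumulative counts, so completing a block cannot undo a limit that has been reached. If patient 1 has a DLT, the condition for the first 5 patients is already met, but a site following the block schedule may treat patients 2 to 5 before anyone is asked to review. Phase I does not work this way: Table 12.1 is applied as each patient becomes evaluable. In Phase II the per-patient check and the stagger both end.

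At stake is how many patients start treatment between the point at which the review becomes certain and the point at which it is held. This matters because Phase I has at most 9 patients across all doses, so part of the safety information on the chosen dose will come from Phase II.

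**Working it through.** **Inputs.** Limits 1/5, 2/10 and 2/15 (Section 12.1); 20 patients (Section 12.5.1); a 5-week DLT window (Section 6.1); 29 patients in 36 months (Section 12.6.1). The true DLT rates used are 5% and 30%, as in the plan, and 20% as an intermediate value. Write p for the DLT rate and q = 1 − p.

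**Step 1: the plan's trigger probabilities.** The rule is not triggered only if there is no DLT in patients 1–5 and at most one in patients 6–15:

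P(trigger) = 1 − q^5 × (q^10 + 10·p·q^9)

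- p = 5%: 1 − 0.7738 × 0.9139 = 0.293
- p = 20%: 1 − 0.3277 × 0.3758 = 0.877
- p = 30%: 1 − 0.1681 × 0.1493 = 0.975

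The stated 5% and 62% do not follow from the printed limits. Reading them as more than 1, 2 and 2 (that is, 2/5, 3/10, 3/15) gives 4.9% at p = 5%, 62.4% at 20% and 88.2% at 30%. That mismatch is a separate point. Here it means only that the intended limits are uncertain, so both readings are carried forward.

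**Step 2: running count against block check.** The count never falls, so a limit reached inside a block is still met at the end of it. The two schedules therefore trigger in exactly the same trials, with the probabilities of Step 1.

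**Step 3: patients between reaching the limit and the check.** This step assumes that each outcome is known before the next patient starts. Only the first trigger in a trial is counted.

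- Block 1 (limit reached at patient i): Σ p·q^(i−1)·(5 − i), i = 1…5.
- Blocks 2 and 3 (second DLT at position j among patients 6–15): q^5 × Σ (j − 1)·p²·q^(j−2)·(e − j), with e = 5 for j = 2…5 and e = 10 for j = 6…10.

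At p = 30%, block 1 gives 0.3×4 + 0.21×3 + 0.147×2 + 0.1029×1 = 2.227. Blocks 2 and 3 give 0.1681 × (0.654 + 0.912) = 0.263. The total is 2.49.

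| True DLT rate | Block 1 | Blocks 2–3 | Expected excess per trial | Given a trigger | Chance of at least one |
|---|---|---|---|---|---|
| 5% | 0.476 | 0.108 | 0.58 | 0.583/0.293 = 1.99 | 23% |
| 20% | 1.638 | 0.361 | 2.00 | 2.000/0.877 = 2.28 | 75% |
| 30% | 2.227 | 0.263 | 2.49 | 2.490/0.975 = 2.55 | 87% |

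Under the more-than limits, the expected excess per trial is 0.06, 0.95 and 1.40.

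**Step 4: sensitivity to accrual.** The planned pace averages 36 months / 29 patients, about 5.4 weeks between starts. That is longer than the 5-week window, so patient order alone describes it. Faster paces were simulated (40,000 trials per setting) with the DLT time assumed uniform over the window and the block check assumed to fall when its last patient completes observation. At p = 30% with the printed limits, the excess is about 4.5, 3.7, 3.3 and 2.5 patients for gaps of 1, 2, 4 and 5.4 weeks. The first three gaps are assumptions, since the plan gives no Phase II pace.

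**The case against.** Four arguments on the other side carry weight.

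- **The limit is a prompt for judgement.** A reader might infer that patients are treated beyond a stopping boundary. The text does not support that. Reaching the count leads to a review, and 1/5 (20%), 2/10 (20%) and 2/15 (13%) all lie below the 30% target toxicity. Table 12.1 gives S (same dose) for 1 DLT in 2 to 5 patients and for 2 DLTs in 4 to 9.
- **Waiting can add information.** A reader might infer that the delay buys nothing. It does not change whether a review occurs, but reviewers who see 1 of 5 or 3 of 5 know more than those who see 1 of 1.
- **The wait is permitted, not required.** One DLT in patient 1 already satisfies the words of the first limit, and nothing bars an earlier review. There is also no excess when the last patient of a block is the one who reaches the limit and the check precedes the next start. So patients can be treated in the interval; the documents do not show that they will be.
- **Oversight continues between checks.** The affected patient's infusion is discontinued (Section 6.1), a physician evaluates patients weekly during infusion (Section 6.2), and serious events of grade 3 and above go to the safety committee (Sections 7.2 and 11.2).

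The last argument does not close the gap. None of these measures applies the cumulative count, Section 11.2 sets no interval for the committee's review, and a DLT need not be a serious adverse event. Checking in blocks of 5 is also a recognised practical choice, so this is an avoidable weakness and not an error of calculation.

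**Conclusion.** The point holds as one of timing. Under the block schedule with undelayed enrolment, further patients can be treated after the review has become certain. With the printed limits, the expected number is 0.58, 2.00 and 2.49 per trial at DLT rates of 5%, 20% and 30%.

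These figures assume that outcomes are known before the next start and that sites wait for the end of the block. They do not assume that the review ends the trial. Faster accrual raises them, and more-than limits lower them. At a DLT rate of 5% the effect is small on either reading of the limits. It becomes material near the design's own 30% target.

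A reader might go further and conclude that the documents call for treatment starts to be withheld until a review is complete. They are silent on this. Section 4 ties Day 1 to 7 days (± 3) before the end of chemoradiation, so any pause could cost a patient already under treatment the planned start. That question must be settled by reconciling the sections; the calculation here does not answer it.

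**What to change.** In Section 12.1, state that the toxicity review is called as soon as the cumulative DLT count reaches the limit for the current block, and not only when the block of 5 is complete. Count by order of enrolment, so that a late DLT in an early patient belongs to that patient's block. Apply this to whatever limits are adopted once the limits and the stated 5% and 62% have been brought into agreement, and say what applies to patients 16 to 20.

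Sections 12.1 and 2.4 should also be reconciled on whether enrolment continues while a review is pending, taking the Day 1 timing in Section 4 into account.

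The running count takes one sentence and leaves the trigger probability the same at every DLT rate. Its cost is unscheduled reviews, some of them resting on very few patients.
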